Feasibility of recruitment, retention, intervention adherence and acceptability (Aim 1). We already plan to track *recruitment and retention* activities. *Intervention adherence.* The web will track and capture details about all activities (e.g., number of logins and amount of and type of contents used). We will also ask intervention participants about motivation and barriers preventing them from using the web. *Acceptability.* We will assess acceptability by asking participants to evaluate the usefulness of with each intervention component,

e.g., personal values, using 5 Ws and H, and rehearsal. Lessons learned and results of this aim will be used to refine our future R01, e.g., recruitment and intervention.

Measures (See above and File Name: Study Survey. shown above). Self-reported data will be collected online using password-protected security-ensured Research Electronic Data Capture (REDCAP).

G. Statistical analysis

Statistical analysis. We will use descriptive statistics to examine variable distributions, check for outliers, and summarize sample characteristics. **Aim 1.** We will (1) conduct content analysis to analyze recruitment, enrollment, retention and intervention adherence logs to identify successful strategies used, (2) review quality of steps generated to achieve goals (using a scoring system), and (3) perform descriptive statistics. We will also perform content analysis (for semi-structure interview questions). **Aims 2, 3, and 4.** **Aim 5.** We will perform descriptive analysis. We will first preform descriptive statistics. Next, we will preform mixed-effects linear modeling. **Missing data.** We will carefully examine the pattern of missing data and conduct appropriate multiple imputation if missing at random is indicated. The mixed-effects modeling allows for missing at random. If missing not at random exists, pattern mixture modeling will be used. Sensitivity analysis will evaluate the robustness of study findings without multiple imputation vs. those with imputation or from pattern-mixture modeling.

Zoom IRB Boilerplate:

Zoom is a secure, user-friendly, cloud-based enterprise videoconferencing service that Ohio State University implemented in 2018. Zoom is accessible to faculty and staff at all Ohio State campuses via <https://carmenzoom.osu.edu> .

This multifaceted video and audio conferencing system supports video and audio conferencing across multiple platforms, including room systems, mobile devices, desktops and telephones.

The Zoom platform at Ohio State University has two main features: Zoom meetings and Zoom webinars.

Designed to support collaboration, Zoom meetings support up to 300 video participants. By default, any participant in a meeting can share their video and audio and utilize the chat feature to exchange messages with participants. The meeting host controls all meeting features, which include mute/unmute participants, screen sharing, recording options, video sharing, remote screen control and participant annotation. Annotation allows participants to draw and highlight on the screen share. Zoom webinar provides access for up to 300 view-only attendees and features live question-and-answer, polling, registration and post-webinar reporting.

Ohio State University Zoom offers both local recording and cloud recording and has a storage capacity of 270 days for recordings. Cloud recording includes an option to produce an audio transcript for a meeting or webinar. The transcript is saved to the cloud as a separate .vtt text file, and the host can elect to display the transcript text within the video itself, similar to a closed-caption display.

Zoom is accessed via Ohio State's single sign-on solution, which provides an environment in which users can authenticate/log in at one time to a central server and connect with web-based services. Meeting security best practices such as waiting lobby, inability to join before host, disabling of sharing for participants, and disabling annotation by participants by default have been implemented.

III. Bibliography

1. Prevention CfDCa. Eligibility and enrollment in the Special Supplemental Nutrition Program for Women, Infants, and Children (WIC)--27 states and New York City, 2007-2008. *MMWR Morb Mortal Wkly Rep*. 2013;62(10):189-193.

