Official Title:	Lifestyle Behavior Weight Loss Intervention
NCT Number:	NCT04649047
Document Name:	Study Protocol and Statistical Analysis Plan
Document Date:	November 18, 2022

Research Protocol

Weight Loss Intervention for Mothers with Young Children

I. Objectives

1. Assess intervention fidelity (dose, delivery, receipt) and acceptability by the study participants
2. Investigate potential intervention impact on the primary (body weight) and secondary outcomes (pants size)
3. Explore potential intervention impact on lifestyle behaviors (diet and physical activity)
4. Explore potential intervention impact on motivation (autonomous motivation, self-efficacy, social support), emotion (emotion control, stress), and cognition (impulsivity).
5. Assess cost of different recruitment approaches

II. Background and Rationale

Low-Income Overweight or Obese Mothers of Young Children: Our Priority Population. In the U.S., nearly 50% of low-income women aged 20-40 years are at high risk for type 2 diabetes, because they live in poverty and are overweight or obese (body mass index [BMI] $\geq 25.0 \text{ kg/m}^2$).¹⁻⁴ One-year postpartum, low-income women have over twice the risk (68-75%) for significant weight retention ($\geq 10 \text{ lbs}$) compared to higher-income women (32%).⁵ Significant postpartum weight retention is a strong predictor for lifelong obesity⁶ and adverse maternal and birth outcomes, such as gestational diabetes and macrosomia⁷⁻¹³ during subsequent pregnancies. Weight gain of $\geq 11 \text{ lbs}$ during young adulthood increases risk for obesity-related conditions including type 2 diabetes,¹⁴ which can be delayed and reduced by weight loss.¹⁵

[figure not shown]

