The study would also be the *first to apply episodic future thinking outside the lab with no in-person component (emphasizing clinical feasibility).* The use of episodic future thinking is more effective for long-term motivation and planning than self-generated thought without episodic future thinking. Episodic future thinking enables individuals to generate detailed goal-relevant scene construction,^{64,88,106,107} whereas self-generated thought without episodic future thinking focuses on behaviors with minimum or no scene construction.¹⁰⁸ With the exception of one “internet plus in-person” four-week intervention,⁸³ all prior episodic future thinking studies have been conducted in lab settings where participants followed intensive and specific scripts directing them through vivid imagination of future events. Thus, the relevance and scalability of episodic future thinking for clinical practice remains speculative. Moreover, prior episodic future thinking studies have only focused on one

form of *episodic future thinking*: episodic simulation (mental representation of the future).⁶⁷ The proposed intervention includes episodic simulation, prediction (benefits for achieving goals), intention (identifying when and where the activity will take place), and planning (generating specific steps rather than general plans for achieving the goal done by prior research), all of which come together to support prospective cognition.¹⁰⁹ Furthermore, the study would be *the first to ask participants to vividly imagine their personal plans followed by enabling them to weekly customize the plans*. This approach supports the sense of volition and choice and fulfilling the psychological needs of the participants, which in turn promotes quality of intervention engagement and outcomes.¹¹⁰ Finally, the study would innovate in *use of participant-generated short reminders to promote cohort retention and intervention dosage*.¹¹¹

A. Research Design

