This pilot quasi experimental design study aims to (1) assess intervention fidelity (dose, delivery, receipt) and acceptability by the study participants, (2) investigate potential intervention impact on the primary (body weight) and secondary outcomes (waist circumference), (3) explore potential intervention impact on lifestyle behaviors (diet and physical activity), (4) explore potential intervention impact on motivation (autonomous motivation, self-efficacy, social support), emotion (emotion control, stress), and cognition (impulsivity), and (5) assess cost of different recruitment approaches. We will enroll 30 overweight or obese women with diverse racial and ethnic backgrounds. All measures will be assessed at baseline (T1) and immediately after the three-week intervention (T2).

B. Sample

Inclusion Criteria. Self-reported

- BMI of 25.0-45.0 kg/m² (calculated using height and weight)
- Current enrollment in government assistant programs (for example, WIC, food stamp (SNAP), or Madicaid)
- 6 weeks - 5 years postpartum
- 18-45 years old
- Fluency in speaking, reading, and writing English
- Ownership of a smart phone with unlimited text messages and internet access
- Committed to a three-week intervention study

Exclusion Criteria. Self-reported

- Current pregnancy or lactation
- Plan to become pregnant during the trial
- Type 1 or 2 diabetes
- Untreated thyroid disease
- Drug or alcohol abuse or dependence within last six months
- Major psychiatric disorder (e.g., schizophrenia, bipolar)
- History of bulimia or anorexia
- Current taking of appetite suppressant or (antipsychotic) medications known to affect body weight
- Current participation in a weight control or drug study
- Current or planned participation in a commercial weight loss program
- Previous weight loss surgery
- Contraindications to physical activity.

Sample size/power. We did not perform a formal sample size calculation but based on our available funding and resources. Because of budget constraint, we think a sample size of 30 women is appropriate for this pilot, which will provide preliminary data for us to apply future NIH R01.

C. Measurement/ Instrumentation

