All participants will be assessed at baseline (T1) and immediately after the three-week intervention (T2). Survey data will be collected online using password-protected security-ensured Research Electronic Data Capture (REDCap), a secure web application for building and managing online surveys and databases. Participants will receive up to \$10 for completing T1 data collection and \$20 for T2 data collection. We will contact participants to verify or clarify survey data, e.g., body weight is entered as 90 (most unlikely because we will enroll overweight or obese women) instead of 190.

Feasibility. We will use our tracking records to assess recruitment and retention. To assess intervention implementation, we will extract data from our study web site that will track and capture details about all activities (e.g., amount of and type of activities completed and percent of participants used type in box). We will record the attendance of individual coaching session. Participants will report their motivation and barriers preventing them from engaging in the intervention activities and evaluate the usefulness of with each episodic

future thinking intervention component. We will also use semi-structure interview questions (up to 20 minutes/an individual interview via zoom) to ask participants to evaluate the intervention. We will use website tracking data, individual coaching session, and results of zoom interview to revise the intervention contents for a future large scale intervention study (R01).

Primary outcome: body weight. We will collect self-reported body weight.

Secondary outcome: waist circumference. We will collect self-reported pants size, which is a good indicator of waist circumference.

Lifestyle behaviors.

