collection activities. Finally, participants will be informed about the purpose of the second zoom meeting. They will also be informed that they must complete the online survey within three weeks of the first Zoom meeting in order to be invited to attend the second zoom meeting.

Second zoom meeting (either audio or video recorded per participant preferences. Participants will be enrolled. First, they will be asked to self-generate 3-5 text messages to remind them to complete the intervention activities and join brief individual coaching via Zoom. Next, they will receive a link to complete part I intervention activities, which will take up to 35 minutes to complete. Participants will use their first and last name, and birthday and own device (e.g., smart phone) to log into the intervention website and complete activities, while the research staff still on Zoom to answer women's questions if they have. After completion of the Part I intervention activities, the research staff will schedule an individual coaching session via zoom with the trained interventionist within the next two days. Participants will be informed that each coaching session will be recorded (either audio or video per their preferences). The recording will be transcribed and be analyzed to help us revise the individual coaching sessions for future studies. We will send a zoom link to participants to join the individual coaching session.

Cohort retention. We will apply our previously successful retention strategies. We will allow temporary lapses as needed (e.g., partial data collection at T2) or extend the time window for data collection. We will monitor the retention rate monthly and keep retention logs by asking participants over the phone about their reasons for dropout and any adjustments that could keep them in the study.

Intervention: A self-directed, web-based lifestyle behavior intervention (tailored to participants' needs). **Intervention mode.** All intervention participants will receive the weekly web-based intervention for three weeks. The intervention includes *three topics*: stress management, healthy eating, and physical activity (Figure 2). **Intervention (long-term) goals.** Participants are strongly encouraged to (1) daily manage stress and emotional reactions using positive strategies, (2) daily eat a diet low in fat and consume less sugary drinks, (3) daily eat a diet high in fruits and vegetables, and (4) walk at a brisk pace for 30 min most days a week.⁵⁶

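### The primary outcome is self-reported weight; the protocol text neither requires a fresh scale reading at T1 or T2 nor records whether the figure was measured or recalled, so reporting error cannot be told from true change.

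*Combined protocol and SAP*

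**What the plan says.** Section C (Measurement/ Instrumentation) defines the primary outcome in one sentence: "We will collect self-reported body weight". Section F says how it is gathered: "Self-reported data will be collected online using password-protected security-ensured Research Electronic Data Capture (REDCAP". The Background describes the approach as having "no in-person component", so no staff-measured weight is planned.

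On timing, section A states: "All measures will be assessed at baseline (T1) and immediately after the three-week intervention (T2". Three weeks is nominal. Section E sets this condition for women: "they must complete the online survey within three weeks of the first Zoom meeting in order to be invited to attend the second zoom meeting". The intervention starts at that later meeting, so T1 can precede the first session by some time. The retention paragraph also allows staff to "extend the time window for data collection" at T2.

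The eligibility list in section B requires a smartphone but does not mention a scale. Section C provides for contacting women to check survey entries. Its example is that "body weight is entered as 90 (most unlikely because we will enroll overweight or obese women) instead of 190".

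Objective 2 reads: "Investigate potential intervention impact on the primary (body weight) and secondary outcomes (pants size". It states no size of change. Section G plans descriptive statistics and a mixed-effects linear model, and its sensitivity analyses concern missing data only. Section F refers to a separate Study Survey file that is not part of the public document.

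**The concern.** Over about three weeks any true change in weight is likely to be a few pounds. Figure 2 puts healthy eating in week 2 and physical activity in week 3, which leaves little time for change to build up. Errors in an unmeasured weight can be of the same order.

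Two kinds of error matter for the group mean. A woman who does not weigh herself at T2 may re-enter her T1 figure, which pulls the mean change toward zero. A woman who estimates her weight after weekly coaching and weekly ratings of her own progress may shade it downward, which produces or enlarges an apparent loss. The two act in opposite directions, so the net direction is unknown.

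The plan describes one group measured before and after. The model in section G estimates the mean change in reported weight and cannot split it into true change and change in reporting. Because the source of each figure is not recorded, the split could not be attempted afterwards either. Section B says these data are to support an R01 application, so the weight result will be read as preliminary evidence.

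**Working it through.** **Inputs from the document.** n = 30 (section B, set by budget without a formal calculation); two reports per woman; no target change, SD, alpha or power. There is no planned figure to reproduce.

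**Assumptions, all illustrative.** True three-week change of -3 lb, with a range of -1.5 to -6 lb (0.5 to 2 lb per week for three weeks). SD of change 3 to 6 lb. Paired t-test, two-sided 0.05.

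**1. Repeated T1 figures.** If a fraction f repeat their T1 weight, independently of their true change D, the observed mean is D × (1 - f).
- D = -3: f = 0.2 gives -3 × 0.8 = -2.4 lb; f = 0.5 gives -3 × 0.5 = -1.5 lb.
- D = -1.5: -1.2 to -0.75 lb.
- D = -6: -4.8 to -3.0 lb.

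**2. Shading at T2.** If T2 reports are lowered by s lb on average, the observed mean is D - s. With D = 0 and s = 1 to 2, the observed mean is -1 to -2 lb. The probability that this is statistically significant when nothing has changed (noncentral t, n = 30) is:

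| SD of change (lb) | s = 1 lb | s = 2 lb |
|---|---|---|
| 3 | 0.42 | 0.94 |
| 4 | 0.26 | 0.75 |
| 5 | 0.19 | 0.56 |
| 6 | 0.14 | 0.42 |

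**3. The two cannot be separated.** An observed mean of -1.5 lb fits a true -3 lb with half the women repeating (-3 × 0.5). It also fits a true zero with 1.5 lb of shading (0 - 1.5).

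**4. Rounding.** For reports rounded to the nearest 5 lb, the error SD is 5/√12 = 1.44 lb per report and 1.44 × √2 = 2.04 lb on one woman's change. Its contribution to the standard error of the mean is 2.04/√30 = 0.37 lb. With a true SD of change of 4 lb, the total SD becomes √(4² + 2.04²) = 4.49 lb, and the mean change detectable with 80% power moves from 2.12 to 2.38 lb. In a simulation with true change -3 lb (SD 2), 41% of women showed no change after 5-lb rounding, yet the mean stayed at -3.0 lb. Rounding blurs individual changes but barely affects the mean.

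**The case against.** Self-report follows from a budget-limited pilot run wholly at a distance, and it is a reasonable choice. Error that is the same at both times, such as habitual under-reporting, cancels within each woman. Both points stand: the issue is the unknown source of each figure, not self-report as such.

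The weight item sits in the Study Survey file, and section E has staff show women how to complete the survey. An instruction to weigh may already exist. That stands too, so the finding is limited to the protocol text. The call-back in section C is also broader than its example, although a check prompted by implausible entries would not reliably find errors of a few pounds.

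No document figure supports the repeat fraction or the size of shading, and the long-term goals and coaching outline name no weight target. The sizes above therefore show what could happen, not what is likely.

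A reader might infer more than the documents support:
- **That reporting error is as large as the change Objective 2 seeks.** Objective 2 gives no size to compare with.
- **That rounding alone could swamp the result.** It largely averages out over 30 women.
- **That a control group would remove the problem.** Shading caused by coaching would be absent in uncoached controls and so would not cancel. Repeating T1 figures equally in both arms would shrink the difference between them.
- **That only women with scale readings should form the main estimate.** That selects on behaviour at T2, since women who believe they have lost weight may be readier to step on a scale.

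**Conclusion.** The point holds for the protocol as written. Weight is the named primary outcome, its source is unspecified and unrecorded, and the single-group design cannot separate true change from repeated or shaded reports. Under the stated assumptions, repeating by 20-50% of women turns a true -3 lb into -2.4 to -1.5 lb, and shading of 1-2 lb turns a true zero into -1 to -2 lb. The direction of any net error is unknown. Rounding is secondary.

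This does not undermine the pilot or call for clinic weighing. It is a cheap improvement to the primary measurement. If the Study Survey file already asks for a same-day reading and its source, the protocol need only say so.

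**What to change.** - **Instruction.** In the T1 and T2 REDCap surveys, ask women who have access to a scale to weigh themselves that day, on the same scale both times, and to enter the displayed figure. The first Zoom meeting, where the survey is already demonstrated, is a natural place to explain this.
- **Source item.** Add one item for the source and date of the weight: scale today; scale earlier, with date; or estimate.
- **Analysis.** Keep all reports as the main Aim 2 estimate. Add a sensitivity analysis restricted to women with same-day scale readings at both T1 and T2.
- **Feasibility.** Report the number of women without a scale reading as an Aim 1 result.

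The cost is one instruction and one item at each of two surveys, with no equipment. The restricted analysis will use fewer women, over-represent scale owners and possibly select women who expect to have lost weight, which is why it should sit beside the main estimate and not replace it.

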A1. Attend information session (first zoom meeting)	Yes	Yes	Up to 3 times
A2. Full consent to participation	Yes	No	Up to 3 times
A3. Attend second zoom meeting	Yes	Yes	Up to 3 times
B. Intervention Phase			
B1: Complete Part I intervention: becoming a better me	Yes	Yes	Need to send both email and text (at the same time) because of including web link—participants can

			complete via smart phone or computer internet access. Up to 3 times for each
B2. Complete Part II intervention: safe care booster	Yes	Yes	Need to send both email and text (at the same time) because of including web link. Up to 3 times for each
B3. Join the weekly individual coaching via zoom	Yes	Yes	Up to 3 times
C. Throughout the project			
C1. Fill out online survey	Yes	Yes	Need to send both email and text (at the same time) because of including web link. Up to 3 times for each
D. Notify Incentives	Yes	Yes	Up to 3 times for each

E. Detailed study procedures

Recruitment and enrollment. Participants will be recruited via four approaches: (1) FaceBook, (2) Study Search, (3) Research Match, (4) MyChart, and (5) study flyer

FaceBook. We will post the study flyer at FaceBook (File name: Flyer_FaceBook Add). Potential participants who are interested in the study will contact the study office for screening.

Study Search. We will post the study flyer at Study Search via OSU Medical Center website (File name: Flyer_study search). Potential participants who are interested in the study will contact the study office for screening.

Research Match. We will post the study flyer at Research Match website (File name: Flyer_Research Match, which describe how participants will be identified in details). The study office will contact the potential participants who are interested in the study.

MyChart. We will post the study flyer at MyChart (via 'OSU BMI', File name: Flyer_MyChart). Upon IRB approval, we will submit an "honest broker data request form" followed by working with 'OSU BMI' to identify potential participants. Once potential participants who are interested in the study are identified, 'OSU BMI' will refer these potential participants to IHIS box. The trained research staff will log into IHIS to contact the potential participants.

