Figure 2. Topics for the three-week intervention. *Stress management* includes three subtopics (e.g., better ways to handle everyday life) and 13 short-term goals (e.g., have a better relationship with family). *Healthy eating* includes four subtopics (e.g., effective ways to reduce junk food intake) and 11 short-term goals (e.g., daily eat less junk food and be mindful what I eat). *Physical activity* has one subtopic and three short-term goals (e.g., being more physically active outdoors).

	Week 1	Week 2	Week 3
Weekly web (up to 40 min/week)	Stress management	Healthy eating	Physical activity
Weekly individual coaching via zoom (15 min/call, 10 calls)	x	x	x

Intervention development based on preliminary work. *Informal interviews with stakeholders.* We informally met with several clinicians who provided prenatal care to the target audience to inform our mode of intervention delivery. They suggested a self-directed, web-based intervention because of its easy implementation and future scalability to overcome clinicians' time constraints to providing additional information on stress management, healthy eating and physical activity to help women manage their weight. **Study one.** We conducted seven focus group discussions with overweight or obese pregnant women (N = 96) to identify their critical needs in stress management, healthy eating, and physical activity. Women reported, for example, poor relationships with significant others, feeling emotional, eating foods for comfort, and lack of motivation to be physically active.¹²³ Results of this study were used to develop the pre-written short-term goals for the participants (Figure 2) because most women had challenges in goal setting. **Study two.** Below, we present lessons learned from our prior NIH-NIDDK R18 intervention study of overweight or obese women of child-bearing age¹²⁴ to develop the two parts of the GOEFT intervention (Figure 3). Part I. *Motivation.* Lesson learned: Personal values and interest (autonomous motivation) motivated women to make positive lifestyle

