Part II (Weekly Days 5-7: 5 min)
Evaluation of Goal Process with Feedback
-Two short-term goals, helpful tips used to achieve the goals, benefits of achieving the goals, four long-term goals followed by personal values
Summary of part II

Participants will use their own device to complete Part II intervention activities for week one and the additional two weeks of the intervention at convenient times and locations. We will send the web link to participants weekly via email and text with an “intervention adherence” text message reminder (generated by the participants) to log in and complete the intervention activities.

Part I (weekly days 1-4, 30-35 min/week): Motivation, emotion and cognition. **Motivation.** Participants will first be asked to visualize, then use a dropdown menu to select their responses (or type in a box) for the following: their personal values and ways to help them commit to and increase confidence in achieving their personal values. **Emotion and cognition.** First, participants will select a subtopic from the week's designated topic (Figure 2) followed by selecting a pre-written short-term goal (or typing in a box) under the chosen subtopic that meets their need for that week's focus. Then, they will visualize and describe WHAT the week's goal is, WHY it is important, WHEN, WHERE, and with WHOM it will take place, and HOW it can be

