Individual coaching session via Zoom (15 min/call, 10 calls). Participants will receive a call within 1-2 days after they complete the Part I intervention activities. All coaching session will be either video or audio recorded (per participants’ preference) with participants’ permission. Participants will be informed that the recording will be transcribed and be used to refine the individual coaching session for future studies. During each call, the research will listen empathetically and use open-ended questions asking participants to visualize and describe how the week’s goals fit with their personal values, thereby supporting their motivation (autonomous motivation).³⁶ Next, participants will be asked to visualize and describe how they will accomplish the goal(s) – what specific steps they will take. Then, the research staff will assess the specificity of the steps and reinforce or help modify the plans (emotion and cognition). Finally, participants will be asked to visualize and describe barriers to implement plans and strategies to overcome barriers. The research staff will assist with problem solving as needed (self-efficacy). We will keep IPC attendance records. Fidelity. [name] and each research will listen to a random 25% of the audio recordings monthly and use the fidelity checklist to assess protocol adherence, strengths, and reasons for deviations.

Intervention adherence. Each week, participants will receive up to three prescheduled text reminders via their smart phone to engage in the week’s intervention activities (until they complete). If women have not completed all activities after seven days, the research staff will call and ask them to complete the activities that they have missed and ask reasons for nonadherence. When a woman expresses interest in quitting some aspects of the intervention activities, we will assess barriers to adherence, brainstorm strategies to overcome barriers, and offer options to reduce intervention adherence burden. We will keep intervention adherence log.

F. Internal Validity

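### The plan states 10 coaching calls, but its own weekly three-week schedule gives 3 calls per woman

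*Combined protocol and SAP*

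**What the plan says.** The number of calls is stated twice in Section E, Detailed study procedures. The coaching row of Figure 2 reads "Weekly individual coaching via zoom (15 min/call, 10 calls", under columns for Weeks 1, 2 and 3 with one mark in each. The coaching paragraph later in the section opens "Individual coaching session via Zoom (15 min/call, 10 calls".

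The timing of the calls is set out in several places:

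- **Message table** (Sent messages to participants, row B3): "Join the weekly individual coaching via zoom".
- **Coaching paragraph:** "Participants will receive a call within 1-2 days after they complete the Part I intervention activities".
- **Second zoom meeting**, after the first Part I: "the research staff will schedule an individual coaching session via zoom with the trained interventionist within the next two days".
- **Frequency of Part I:** "Part I (weekly days 1-4, 30-35 min/week".
- **Length of the intervention** (Intervention mode): "All intervention participants will receive the weekly web-based intervention for three weeks".
- **Assessments** (Section A, Research Design): "All measures will be assessed at baseline (T1) and immediately after the three-week intervention (T2".

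Section I lists intervention fidelity, broken down into dose, delivery and receipt, as the first objective. Section C (Feasibility) says that attendance at coaching will be recorded. For Aim 1, Section G plans content analysis of the logs and descriptive statistics.

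**The concern.** A weekly call over three weeks is 3 calls. The Figure 2 row contradicts itself: its label says weekly, its columns stop at Week 3, and its count is 10. Because the coaching paragraph repeats the count, this is not an isolated slip in a table.

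Assessing dose and receipt needs a defined planned dose, and 10 is the only explicit total of coaching calls in the intervention procedures. Coaching is also one of the two components that the Conceptual Framework presents as distinguishing this intervention from earlier work. The results are meant to shape a larger trial, and the rationale stresses scalability and limited staff time. A reader who takes 10 at face value would believe that the pilot tested more than three times the coaching contact its schedule can deliver.

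**Working it through.** **Inputs**

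- Stated count: 10 calls of 15 minutes (Figure 2 and the coaching paragraph, Section E).
- Frequency: one per week (Figure 2; message table, row B3).
- Trigger: one call after Part I (coaching paragraph; Second zoom meeting), and Part I is done once a week.
- Duration: three weeks (Intervention mode), with T2 immediately afterwards (Section A).
- Sample: 30 women in a single group (Section A).

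**Trying to reproduce 10**

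| Way of counting | Arithmetic | Result |
|---|---|---|
| One call per week | 1 × 3 | 3 |
| One call per completed Part I | 1 × 3 | 3 |
| One call per short-term goal (two a week) | 2 × 3 | 6 |
| One call after each of Part I and Part II | 2 × 3 | 6 |
| Coaching plus the two enrolment Zoom meetings | 3 + 2 | 5 |
| The same plus the evaluation interview | 3 + 2 + 1 | 6 |
| Maximum weekly reminders (up to three) | 3 × 3 | 9 |
| Study total across all women | 30 × 3 | 90 |

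None gives 10. The two rows that follow the plan's own rules both give 3.

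**Whether 10 could fit the timetable**

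- At one call a week, 10 calls take 10 weeks. T2 follows week 3, so 10 − 3 = 7 calls would come after T2.
- Within three weeks, 10 ÷ 3 ≈ 3.3 calls a week would be needed, against one Part I trigger a week.

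**Size of the discrepancy**

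- Calls per woman: 3 against 10, a difference of 7.
- Coaching time per woman: 3 × 15 = 45 minutes against 10 × 15 = 150 minutes.
- Calls for the whole study: 30 × 3 = 90 against 30 × 10 = 300.
- Attendance share, only if 10 were used as the denominator: a woman who attends every scheduled weekly call would score 3 ÷ 10 = 30% instead of 3 ÷ 3 = 100%.

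**The case against.** The strongest reply accepts the contradiction and disputes its weight. Nothing in the plan uses 10 as an input. There is no formal sample size calculation, no endpoint or stopping rule depends on the count, and no coaching-dose percentage is specified. The operating instructions agree with one another, so staff who follow them would deliver a coherent intervention. The 30% and the 7 calls after T2 both rest on scenarios that the plan does not propose. A mark in a week column does not by itself cap the calls at one, and the Scientific Premise describes the calls only as periodic. On this view it is a wrong number in two parentheses.

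Much of this stands. The effect is confined to the stated dose, both of those figures are conditional, and 3 is inferred. The reply does not remove the problem, however. The weekly label and the Part I trigger, taken with the three-week length, leave no room for 10. A pilot whose first objective includes dose should state the planned dose of a core component correctly.

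It is also fair to say that the correction is trivial only if 3 is right. If 10 is intended, staff would hold 300 calls instead of 90. Reviewing 25% of recordings would then mean 0.25 × 300 = 75 instead of 0.25 × 90 = 22.5, or about 23, if every call is held and recorded.

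**Conclusion.** The concern holds. The stated 10 calls cannot be reconciled with the plan's own schedule, which gives 3 calls (45 minutes) per woman instead of 10 (150 minutes). The documents prove the contradiction. That 3 was intended rests on reading one call per weekly Part I over three weeks, which every timing rule supports but no sentence states as a total.

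The consequence is limited to the described intensity of the intervention and to any coaching-dose percentage someone might later compute. Raw attendance counts, the 25% sampling rule for the fidelity review and the weight analyses are unaffected. It should be corrected, but it does not threaten the trial's main results.

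**What to change.** Ask the sponsor to confirm the intended number. If it is 3, as the schedule implies, replace 10 with 3 in the coaching row of Figure 2 and in the coaching paragraph of Section E. Suitable wording would be: three calls of 15 minutes, one each week after Part I. Name that count as the planned coaching dose when dose and receipt are described under Aim 1, so that attendance is reported against 3. This costs two wording changes and needs no new data or analysis.

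If 10 is intended, rewrite the weekly schedule and the call trigger so that all 10 calls occur before T2, and budget for the extra staff time.
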